 - i. The size of the injury will be measured in centimetres with a sterilized scale.
 - ii. The site of injury can either be the dome of the bladder, the posterior bladder wall, the trigone or one or both ureters.
 - iii. Depth of injury will be taken as layers involved i.e. either involving muscular layer partly or completely with intact mucosa or full depth injury (perforation).
 - iv.

Operative Time: The staff nurse will record the duration of surgery as time in minutes from incision to closure of the skin.

Blood Loss: The estimated blood loss will be determined by the increase in weight of sponges used during the operation, taking 1 gram equal to 1cc of blood and the number of subjects who received blood transfusion during operation.

Secondary Outcomes

Postoperatively, subjects will be assessed for urinary tract infection (UTI), micturition problems, and fistula formation during the hospital stay and for the next three months. Duration of catheterization and hospital stay will also be recorded. The outcome of each subject will be noted on a Performa by assigned medical officers during the hospital stay and the follow-up period and entered in SPSS20 datasheet.

1-Urinary tract infection (UTI) markers will be more than 10pus cells/hpf in urine or urine showing infectious organisms on culture on the third postoperative day.

- A. **Dysuria** will be expressed by the subject as painful micturition using an 11point Numeric Rating Scale ICCs (.673-.825), $r=.7-.99$. (0 No Pain, 1-3 Mild Pain, 4-6 Moderate Pain, 7-10 Severe Pain).
- B. **Other micturition problems** (feeling of incomplete evacuation, frequency, urgency, urethral and extra-urethral incontinence) will be measured subjectively on Likert scale questionnaire (0-never, 1-rarely, 2-sometimes, and 3-often) and analyzed as a composite variable in spss. Urinary retention will be diagnosed if post-micturition bladder volume is >50cc on ultrasonography on the day of discharge from the hospital.

- I. **Feeling of incomplete evacuation:** It is the feeling created by incomplete emptying of the bladder. The subject will be inquired about the feeling of full bladder accompanying it.
- II. **Urgency** will be diagnosed as a sudden urge to urinate.
- III. **Frequency** Needing to pass urine more than seven times in 24hours.

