[name] is the Corresponding Author and chief investigator. She has conceived the project and she will write and review the manuscript and will create Figures and tables. She will hold a monthly meeting of the research team to evaluate any difficulties encountered with study design and to find a solution to the problems.

[name] will counsel the subjects, participate in preparing random numbers file, conduct surveys to collect preoperative and postoperative data in wards, participate in Manuscript writing and review the manuscript.

[name] will counsel the subjects, participate in preparing random numbers file, manage cysto-inflation in theatre, perform follow up of the subjects and conduct the survey in the hospital to collect data after discharge, and will review the manuscript.

[name] will collect all preoperative and postoperative data, enter it into SPSS data sheet and hand it over to statistician and review the manuscript.

[name] will perform statistical calculations and will review the manuscript.

Collaboration with other scientists: To avoid Bias, the research team will shift data in spss datasheet to [name] for the compilation of results on an individual level.

A randomized controlled trial of CystoInflation to prevent bladder injury in the adhesive disease of multiple caesarean sections

ENTRY FORM OF CYSTOINFLATION STUDY

Country	Pakistan
Hospital	Lady Willingdon Hospital
Unit	1

Patient Profile

Patient name	
Age	
Gestational age	
Parity	
Socioeconomic status	
BMI	

Examination

Pulse	
BP	
Temperature	
Pallor	
Chest	
CVS	
P/A	

Investigations

Blood Group	
C/E blood	
C/E Urine	
BSL(F)	
Obstetric USG	

Randomization

Date of operation	
Time of operation	
Grade of adhesions	
Eligible	
Consent for study	
Random number	
Signature of the Principal	

surgeon	
---------	--

- Store the original completed form in the Principal investigator study file.

A randomized controlled trial of Cysto-inflation to prevent bladder injury in the adhesive disease of multiple caesarean sections

OUTCOME FORM

Operative Findings

Bladder injury	No	Yes
Size		
Site		
Depth		
Operative time		
Blood loss		
blood transfusion		
Operative time		
Blood loss		
blood transfusion		

Postoperative Follow up on 3rd postoperative day

Follow up	No	Yes
WBC count		
Urine culture	_ive	+ive

fever	No					Yes					
Dysuria	0	1	2	3	4	5	6	7	8	9	10
Frequency of micturition	0				1			2			3
Urgency of micturition	0				1			2			3

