Feeling of urinary retention	0				1			2			3
Urethral incontinence	0				1			2			3
fistula	No					Yes					

Postoperative Follow up on the day of discharge from hospital

Follow up	No					Yes					
Postoperative Postmicturition bladder volume											
fever	No					Yes					
Dysuria	0	1	2	3	4	5	6	7	8	9	10
Frequency of micturition	0				1			2			3
Urgency of micturition	0				1			2			3
Feeling of urinary retention	0				1			2			3
Urethral incontinence	0				1			2			3
fistula	No					Yes					

Postoperative Follow up from 1-6weeks

Came for follow up	No					Yes					
fever	No					Yes					
Dysuria	0	1	2	3	4	5	6	7	8	9	10
Frequency of micturition	0				1			2			3
Urgency of micturition	0				1			2			3
Feeling of urinary retention	0				1			2			3
Urethral incontinence	0				1			2			3
fistula	No					Yes					

Postoperative Follow up from 6weeks -3months

Came for follow up	No					Yes					
fever	No					Yes					
Dysuria	0	1	2	3	4	5	6	7	8	9	10
Frequency of micturition	0				1			2			3
Urgency of micturition	0				1			2			3
Feeling of urinary retention	0				1			2			3
Urethral incontinence	0				1			2			3
fistula	No					Yes					

Follow up at the end of 3months

Came for follow up	No					Yes					
fever	No					Yes					
Dysuria	0	1	2	3	4	5	6	7	8	9	10
Frequency of micturition	0		1		2		3				
Urgency of micturition	0		1		2		3				
Feeling of urinary retention	0		1		2		3				
Urethral incontinence	0		1		2		3				
Fistula confirmed by retrograde cystography	No					Yes					

Figure 1:

[figure not shown]

Figure1. Consort Diagram. Patient assignment to groups, follow up and analysis

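### The Outcome Form has four of the five items in the micturition composite, no field for catheter duration or hospital stay, and a day-3 white-cell row without specimen or unit

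*Combined protocol and SAP*

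**What the plan says.** Secondary Outcomes, item B, lists the symptoms "feeling of incomplete evacuation, frequency, urgency, urethral and extra-urethral incontinence". Each is scored on a four-point scale from 0 (never) to 3 (often), and together they are "analyzed as a composite variable in spss". No rule for combining them is given. The same item defines urinary retention separately, as a post-micturition volume above 50 cc on ultrasound on the day of discharge.

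For urinary tract infection, the "markers will be more than 10pus cells/hpf in urine or urine showing infectious organisms on culture", assessed on the third postoperative day.

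The opening paragraph of Secondary Outcomes adds: "Duration of catheterization and hospital stay will also be recorded".

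The Outcome Form has five follow-up blocks: day 3, discharge, 1-6 weeks, 6 weeks to 3 months, and the end of 3 months. In each, the rows scored 0-3 are "Frequency of micturition", "Urgency of micturition", "Feeling of urinary retention" and "Urethral incontinence". Each block also has a 0-10 dysuria row and a No/Yes fistula row.

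Secondary Outcomes sends outcomes to a proforma and then to the SPSS datasheet. The Documents safety paragraph of the Data Management Plan likewise says that variables are entered from the completed forms.

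**The concern.** The forms are the only stated route from the patient to the dataset, so an outcome with no field is not collected when the plan is followed as written. A symptom score that was not asked for at a visit cannot be rebuilt reliably afterwards.

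Three things are at stake. The composite that is analysed would not be the one defined. Two listed outcomes would depend on an unplanned search of other records. The pus-cell half of the infection definition would depend on how each medical officer reads an unlabelled row. Urinary morbidity matters in this trial: the Background itself raises postoperative micturition problems as a risk of over-distending the bladder.

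**Working it through.** No power, alpha or sample-size figure bears on this point, and the plan gives no figure to reproduce. The check sets the definitions in Secondary Outcomes beside the rows of the two forms.

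| Defined in Secondary Outcomes | Row on the forms | Match |
|---|---|---|
| Frequency, 0-3 | "Frequency of micturition", 5 of 5 blocks | Yes |
| Urgency, 0-3 | "Urgency of micturition", 5 of 5 blocks | Yes |
| Urethral incontinence, 0-3 | "Urethral incontinence", 5 of 5 blocks | Yes |
| Incomplete evacuation, 0-3 | "Feeling of urinary retention", 5 of 5 blocks | Collected under another name |
| Extra-urethral incontinence, 0-3 | None in any block; nearest is fistula, No/Yes | No |
| Retention by ultrasound volume | Post-micturition volume, discharge block | Yes |
| Pus cells per high-power field, day 3 | White-cell count, day 3; no specimen, unit or threshold, under a No/Yes header | Ambiguous |
| Urine culture, day 3 | Urine culture, negative/positive | Yes |
| Catheter duration | None; no removal date | No |
| Hospital stay | None; no discharge date | No |

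**Composite.** Five items are defined and four are collected, in five of five blocks. What this does to the score depends on a combining rule that the plan does not state. Three possible rules, each an assumption:

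- Simple sum: 5 × 3 = 15 as defined and 4 × 3 = 12 as collectable, so the range is 0-15 against 0-12.
- Mean of items: 15/5 = 3 and 12/4 = 3. The range is the same, but the content differs.
- Any problem, yes or no: the range is the same, but a woman whose only complaint is extra-urethral leakage counts as yes under the definition and no on the form.

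The defined composite cannot be built under any of these. The 0-15 against 0-12 contrast holds only under the first.

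**Duration and stay.** Each needs an end date minus a start date. The Entry Form has the date and time of operation. Neither form has the date of catheter removal or of discharge, so neither difference can be computed from the forms.

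**White-cell row.** The Entry Form separates the blood examination from the urine examination; the Outcome Form's white-cell row does not. It stands directly above urine culture, which favours a urine reading but does not settle it, and nothing asks for a count per high-power field.

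**Extraction.** The form was read from PDF. The same four rows recur in all five blocks, so a row lost in reading is an unlikely explanation.

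**The case against.** The strongest case on the other side is that little of clinical weight is lost.

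- **Fistula.** A reader might infer that without an extra-urethral row the trial would miss its most serious urinary harm. The documents do not support that. Every block has a fistula row, women who complain of incontinence have a three swab test and cystography, and all women are due cystography at the mandatory three-month visit. What is lost is one symptom item.
- **Pus cells.** A reader might infer that they have no field, or that a blood count would be entered. The row's place above urine culture makes urine white cells the natural reading, and the officers who fill in the form are to be trained. The row is ambiguous, not absent.
- **Retention.** The form row is a subjective feeling, and ultrasound volume has its own row at discharge. The two outcomes are not merged; this is a naming mismatch.
- **Masking.** A reader might infer that more leakage could be hidden by less frequency in the composite, and that the composite is the only analysis of these items. The first assumes a simple sum, which is not stated. The second overlooks Statistical analysis, which plans numbers and percentages for outcomes, then regression, and enters a repeated problem only once. Whether the composite should rank below its items is a matter of preference.
- **Duration and stay.** The text largely fixes both by injury depth and size, which the form records. The random number is also written on the hospital admission file, so dates might be traced.

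These replies stand, except that the last goes only part of the way. A scheduled duration is not an observed one, discharge after catheter removal depends on the woman having no urinary complaint, and nowhere does the plan say that the admission file will supply these outcomes.

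**Conclusion.** The point holds as an inconsistency between the outcome definitions and the form. One of five composite items has no 0-3 row in any of the five blocks, and another carries a name that the text uses for a different outcome. Two listed secondary outcomes have no field on either form. One of the two criteria for urinary tract infection rests on an ambiguous row. This applies to all 214 planned women.

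The conclusion assumes that the forms in the document are the ones to be used and that no other record feeds the dataset; the plan describes none. It does not reach the primary outcomes, the sample size or the randomisation, and it does not mean that fistulas would go undetected. The missing combining rule is a gap in its own right, and any numerical range for the composite depends on how it is filled. The mismatch should be corrected, because the repair is cheap and symptom scores that were never collected cannot be recovered reliably.

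**What to change.** 1. Add a 0-3 row for extra-urethral incontinence to each of the five blocks, or remove that item from the composite definition.
2. On the form, use the name that Secondary Outcomes gives to incomplete evacuation.
3. Relabel the day-3 white-cell row as urine pus cells per high-power field, with a numeric entry.
4. Add the dates of catheter removal and discharge. If stay is to be counted from admission and not from operation, add the admission date too, since the Entry Form shows only the operation date.
5. State in Secondary Outcomes how the micturition items are combined into one variable.

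The cost is a form reprint, a few more fields for the medical officers to fill in and a sentence or two of text. No clinical procedure changes.

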- IV. **Vesicovaginal or uretro-vaginal Fistula:** In subjects with the complaint of urinary incontinence, the fistula formation i.e. abnormal communication of urinary bladder or ureter with vagina will be ruled out by three swab test and retrograde cystography. The follow up of fistula cases is outside the scope of this study so it will not be included in description or analysis.

C. **Duration of Foleys catheter and hospital stay:** The Foley's catheter will be removed after 24 hours in distension arms of both groups and subjects stay in the hospital for four days. In the bladder injury arms, the catheter will be kept in situ for 7days to give rest to the bladder for the healing of repair of muscularis disruptions, for 10 days in case of repair of perforations smaller than 1cm, and for 14 days for repair of perforations greater than 1cm. After removal of the catheter, the subjects will be kept in the hospital for twelve hours and then discharged if there will have no subjective urinary complaint.

The finding of subjects will be noted on output form by assigned trainees. The participant's first entry on follow up form will be completed on the third postoperative day; second entry will be at the time of discharge from the hospital and last entry at the end of three months postoperative period. In between, they will be advised to visit our team whenever a problem emerges during the postoperative period and their findings will be recorded on the output form. In subjects complaining of urinary incontinence, the fistula formation will be ruled out first by three swab test and then by retrograde cystography. The postoperative visit at the end of 3months will be mandatory. During this visit, all the subjects will be analyzed for postoperative micturition problems and their retrograde cystography will be performed to rule out fistula formation. The subjects with fistula will be referred to the urologist for further management. The last entry at the end of three months will also be mandatory for the inclusion of participant outcome after discharge in results. The participants will be advised to visit the researcher team at the end of 3months period. They will be reminded for their visit on phone call after week if they do not come for follow-up (See [Outcome](#)).

Statistical analysis

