We will perform Statistical analysis by using IBM spss statistics 20 (SPSS Inc, Chicago, IL, USA). The characteristics of the subjects will be analyzed as continuous data or ordinal data. Normality of continuous data will be analyzed by the Shapiro Wilk test. The normal baseline data will be compared by T-test, non-normal data by Mann Whitney U test and ordinal data with the chi-square test. The outcome of both groups will be calculated as numbers (percentages) by descriptive statistics. The effect of cysto-inflation on outcome data will be analyzed using regression analysis. The same problem experienced by the same subject will be recorded only once on the spss datasheet. There will be no second entry if the subject presents with the same problem again. The data for any subject who do not come for follow up after discharge will be used and analyzed in study characteristics but will be excluded from the analysis of results. The power of the study for bladder injury will be calculated with statistical software G'Power version 3.1.

Adverse events

The study team will be responsible to record all adverse events and serious adverse events to the subjects of the study, related to or not related to the intervention. The team members will ask open probing questions to enhance the quality of the collected data. An adverse event is

defined as any undesirable experience during follow-up leading to contact with the healthcare system (general practitioner or hospital). If adverse event results in hospitalisation, prolonged inpatient hospital care, result in re-surgery, or if an adverse event is life-threatening, result in death, permanent disability or damage, they will be categorised as serious adverse events. Adverse Events will be recorded in the adverse events reporting register. The study team will report all expected and unexpected adverse events in the study population to the principal investigator in monthly meetings to assess their potential consequences.

Data Management Plan

Documents safety

All the documents, together with the numbered envelopes and the completed forms will be stored in folders that will be kept in the locked research office of the principal investigator with access limited to authorised persons. The study team will ensure that all variables from the completed forms are continuously entered into SPSS 20 datasheet.

Data monitoring

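### Urinary retention is diagnosed only on the day of discharge, so retention that resolves earlier, even if it needed re-catheterisation, is not counted as retention

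*Combined protocol and SAP*

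**What the plan says.** Secondary Outcomes, item B (Other micturition problems), defines retention by a single measurement: "Urinary retention will be diagnosed if post-micturition bladder volume is >50cc on ultrasonography on the day of discharge from the hospital". The Outcome Form matches this. Its row "Postoperative Postmicturition bladder volume" appears in the day-of-discharge block and in no other follow-up block.

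Item C (Duration of Foleys catheter and hospital stay) sets the timing. The catheter is "removed after 24 hours in distension arms of both groups and subjects stay in the hospital for four days". I read this as the schedule for women without bladder injury, because the next sentence sets 7, 10 or 14 days for injured women. After those longer periods, "the subjects will be kept in the hospital for twelve hours and then discharged if there will have no subjective urinary complaint".

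Three other records bear on retention:

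- Secondary Outcomes states: "Duration of catheterization and hospital stay will also be recorded".
- The Outcome Form scores "Feeling of urinary retention" from 0 to 3 in every follow-up block. The item B symptoms, which include a feeling of incomplete evacuation, are to be scored on the same scale "and analyzed as a composite variable in spss".
- The Adverse events section defines an event as "any undesirable experience during follow-up leading to contact with the healthcare system (general practitioner or hospital").

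Baseline Data lists the preoperative post-void bladder volume as a characteristic to be collected. Statistical analysis compares baseline data between groups and plans regression for the effect on outcomes, without naming covariates.

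**The concern.** The intervention fills the bladder with 300 cc. The Background says that over-distension can lead to retention, and that filling only during adhesiolysis and within normal capacity avoids this. The discharge scan is the plan's only objective check of that statement.

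The first opportunity for retention to show is when the catheter comes out, at 24 hours in most women. The diagnosis looks only at the last day of the stay. Retention serious enough to need a new catheter, but over by discharge, is classed with normal voiding. If the fill causes mainly short-lived retention, the trial could report the technique as safer on this point than it was.

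A second, smaller matter is that the 50 cc threshold is applied without regard to the woman's own preoperative volume. Women are excluded for urinary complaints, not for a measured volume, so a woman without symptoms who was already above 50 cc could be counted as a postoperative case.

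**Working it through.** The plan states no retention rate and no figure to reproduce, so the check is mainly one of timing and of what each record feeds into.

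1. **Removal to scan, uninjured women** (item C). Four days of 24 hours, less 24 hours: 96 − 24 = 72 h. If the operation day counts as day one: 72 − 24 = 48 h. The plan states no hour, so 48 to 72 h is nominal.

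2. **Where a volume is recorded** (Outcome Form). There are five follow-up blocks: day 3, discharge, 1 to 6 weeks, 6 weeks to 3 months, and end of 3 months. A volume row appears in 1 of the 5.

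3. **Course of one patient.** Catheter out at 24 h; unable to void on day 1 or 2; catheter replaced, then removed; volume of 50 cc or less on day 4. Under item B she has no retention. Nothing in the plan mentions re-catheterisation or makes it count.

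4. **Do the other records change her classification?**
   - Catheter duration: a second period could lengthen it, but no rule says how re-insertion is counted, and the item is separate from retention.
   - Day-3 symptom score: it may be raised, but it is subjective and does not enter the diagnosis.
   - Adverse events: the definition turns on contact with the healthcare system, which does not clearly cover a woman already on the ward. Even if recorded, the event would not become a retention case.

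5. **Number of women, assumed rates.** With 107 per arm (Sample size): 107 × 1% = 1.07 and 107 × 5% = 5.35.

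6. **Effect on a comparison, assumed rates.** Let a share f of true cases persist to discharge, the same in both arms. Then observed difference = f × true difference. Power for a two-sided 5% test, with n = 96 per arm (107 × 0.9 = 96.3), is approximately

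   Φ{[d − 1.96 √(2p̄(1 − p̄)/n)] / √([p₁(1 − p₁) + p₂(1 − p₂)]/n)},

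   where d is the observed difference and p̄ is the mean of the two observed rates.

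   | True rates | f = 1 | f = 0.5 | f = 0.25 |
   |---|---|---|---|
   | 10% v 25% | 0.785 | 0.451 | 0.244 |
   | 5% v 15% | 0.638 | 0.355 | 0.197 |

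   For 10% v 25% with f = 0.5 the observed rates are 5% and 12.5%, so d = 0.075 and p̄ = 0.0875. The two standard errors are 0.0408 and 0.0404, giving Φ(−0.12) = 0.45. The table shows only how sensitivity falls as cases resolve; none of the rates comes from the documents.

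**The case against.** The best defence is that retention still present at discharge is a legitimate endpoint. It is objective, and it is scheduled alike for uninjured women in both arms. The fill stays within the capacity that the Background gives and is drained after adhesiolysis. The plan also assesses micturition problems throughout the hospital stay, asks for all adverse events with open questions, and treats prolonged inpatient care as serious. An early event may well leave a trace. All of this stands, and it limits the point to what the definition counts.

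Four stronger readings are tempting, but the documents do not support them:

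- **The preoperative volume is unused.** It is a listed baseline characteristic and falls under the planned between-group comparison. It is absent only from the retention definition and from any stated adjustment. Randomisation balances it in expectation.
- **The outcome will show no difference between arms.** That needs every excess case to resolve before discharge. With partial persistence the difference shrinks but does not vanish.
- **The scan timing biases the comparison because injured women are scanned sooner after removal.** Uninjured women follow one schedule in both arms. For the rest, the documents give neither the injury rate in dense adhesions nor any retention rate, so neither a direction nor a material size can be shown.
- **The missing form rows prove that the data will not be collected.** The forms as reproduced also lack other promised items, such as number of previous caesareans and hospital stay. Likewise, treating the form's retention-feeling item as part of the item B composite is an inference; it has its own row and could be tabulated alone.

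**Conclusion.** The point holds as a minor one. As defined, retention that resolves before discharge is not counted, even where a catheter had to be replaced, and no other record feeds the diagnosis. The consequence is reduced sensitivity in one secondary safety outcome. Any difference between arms is understated to the extent that cases resolve before the scan, taking the share that resolves to be similar in the two arms. No primary outcome is affected.

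The timing and the form content come from the documents. The size does not: 1.1 to 5.4 women per arm rests on an assumed 1% to 5%. Re-catheterisation is a plausible scenario rather than something the plan describes. The preoperative volume is a missed chance to adjust, not a source of bias.

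**What to change.** Keep the discharge scan and its threshold, and make two additions.

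1. Add one sentence to item B: any re-catheterisation for inability to void after the first catheter removal also counts as retention. Add one Outcome Form row for it (yes/no, date, reason).
2. Name the preoperative post-void volume as a covariate in the planned regression when retention is the outcome, and make sure that the Entry Form captures it.

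The cost is one sentence in the definition, one covariate named in the analysis text, one Outcome Form row and, if it is not already there, one Entry Form field. No scan is added beyond those already promised.

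There are downsides. The recorded retention rate may rise. The reason for re-insertion must be written down, so that catheters replaced for other causes are not counted. The outcome then combines a measured volume with a ward decision; the Blinding section intends staff outside the theatre to be unaware of the group, which limits the scope for that decision to differ by arm. Reporting the two components separately beside the combined figure would keep the discharge result visible.

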Method: We will find out the effectiveness of cystoinflation by conducting a prospective randomized controlled trial in Lady Willingdon Hospital, a university-affiliated teaching hospital in Pakistan, for two years, including a follow-up period of three months. The subjects of the study will be two hundred and fourteen healthy pregnant women with previous operative deliveries which during their C-section, prove to have dense bladder adhesions. The subjects will be randomized into cystoinflation and control groups. Preoperatively, the study team will counsel the women and take informed consent to include them in the study if dense adhesions were found during their C-section. The surgeon will perform adhesiolysis after identifying bladder during retro-fill (with 300cc saline) in the cystoinflation group and without retro-fill in control. The primary outcome will be assessed by bladder injury rate, blood loss and operative time and secondary outcome by postoperative urinary tract infection, micturition problems and fistula formation. Cystoinflation will be considered effective if the proportion of bladder injury in cystoinflation group will be less than 50% of the control.

Discussion: The routine practice of preoperative insertion of urinary catheter fails to prevent bladder injury in multiple C-sections. A few scientists have successfully used cystoinflation technique to prevent bladder injury in pelvic adhesive disease. In this study, we have used cystoinflation in dense adhesions of previous C-sections. The findings of this study may support the previous studies and may serve as a trigger for ongoing research of surgical techniques to prevent iatrogenic bladder injury.

Study protocol: “A controlled study of Cystoinflation to prevent bladder injury in the adhesive disease of multiple caesarean sections”

erb registration: The institutional review board of King Edward Medical University, Pakistan
Reg # 216/RC/KEMU.

Principal Investigator: [name], FCPS; Obstetrics & Gynaecology. Assistant Professor (Obstetrics & Gynaecology), King Edward Medical University /Lady Willingdon Hospital, Lahore, Pakistan

Co-Investigators:

- [name], MS trainee (Obstetrics & Gynaecology), King Edward Medical University /Lady Willingdon Hospital, Lahore, Pakistan
- [name], FCPS trainee (Obstetrics & Gynaecology), King Edward Medical University /Lady Willingdon Hospital, Lahore, Pakistan

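### A fistula confirmed after discharge but before three months is left out of the secondary-outcome analysis if the woman has no three-month entry

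*Combined protocol and SAP*

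**What the plan says.** The Project summary (Method) lists "secondary outcome by postoperative urinary tract infection, micturition problems and fistula formation". The opening of Secondary Outcomes sets the window: "fistula formation during the hospital stay and for the next three months".

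Item IV of that section defines vesicovaginal and ureterovaginal fistula, gives the work-up for women who report incontinence, and ends: "The follow up of fistula cases is outside the scope of this study so it will not be included in description or analysis".

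The follow-up paragraph after item C contains four relevant provisions:
- Between scheduled entries, "they will be advised to visit our team whenever a problem emerges during the postoperative period", and the findings go on the form.
- The visit at three months is mandatory, with cystography for all subjects and a telephone reminder for those who do not come.
- Women found to have a fistula are passed on to a urologist.
- "The last entry at the end of three months will also be mandatory for the inclusion of participant outcome after discharge in results".

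The Statistical analysis section adds a related rule. A woman who does not come for follow-up after discharge stays in the description of study characteristics "but will be excluded from the analysis of results".

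The Outcome Form has a fistula Yes/No item in every follow-up block: day 3, discharge, 1 to 6 weeks, 6 weeks to 3 months, and three months.

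**The concern.** The plan expects some fistulas to appear before three months and provides a work-up and a form field for them. It then makes use of that information depend on a later, separate entry. An event that has been observed, confirmed and recorded can be discarded because a subsequent visit did not happen.

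The Background lists fistula among the consequences of unrecognised bladder perforation, so it bears directly on whether the technique is safe and useful. Events will probably be few. With counts that small, losing one or two can decide whether the report says that no fistula occurred in an arm.

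**Working it through.** The plan states no figure for fistula, so there is none to reproduce. The check is a reading of the rules together, followed by an illustration of scale.

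**Step 1. Apply the rules to four women.**

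| Woman | Last-entry rule (Secondary Outcomes) | Non-attender rule (Statistical analysis) | Fistula counted? |
|---|---|---|---|
| Fistula found before discharge, no later visit | Does not apply (covers outcomes after discharge only) | Excluded on its broad wording | Unclear |
| Fistula confirmed at week 3, attends at three months | Satisfied | Satisfied | Yes |
| Fistula confirmed at week 3, no three-month entry | Excluded | Arguably not excluded, since she did come after discharge | No under the last-entry rule |
| Fistula first seen at the three-month cystography | Satisfied | Satisfied | Yes |

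The third row is the problem. The two rules also disagree about her, and nothing says which governs. No section says that an earlier confirmed fistula still counts.

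**Step 2. How many women the rule could reach.** Inputs are 214 women (107 per group) and a 10% dropout allowance, both from Sample size. Assume that dropout means no three-month entry. Then 0.10 × 214 = 21.4, about 21 women, or 0.10 × 107 = 10.7, about 11 per group. Their post-discharge outcomes would be out of the results, whatever had been recorded at interim visits.

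**Step 3. Chance of losing an observed fistula.** Let k be the number of fistulas confirmed after discharge and before three months. Let q be the probability that such a woman has no three-month entry, independently of the others. The documents give neither, so both are assumed. P(at least one lost) = 1 − (1 − q)^k.

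| k | q = 10% | q = 30% | q = 50% |
|---|---|---|---|
| 1 | 10% | 30% | 50% |
| 2 | 19% | 51% | 75% |
| 3 | 27% | 66% | 88% |

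For example, with k = 2 and q = 30%, 1 − 0.7² = 0.51.

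**Step 4. Effect on a reported rate.** Suppose two such fistulas occur in one arm and none in the other: 2/107 = 1.9% against 0/107. If both women lack the last entry and everyone else has it, the report reads 0/105 against 0/107. This is an illustration, not a forecast.

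**Step 5. Direction.** The rule also removes women without fistula who miss the visit, so the denominator falls too. If women with a fistula attend less often than others, the reported rate is too low. If they attend more often because they have a problem, it is too high. The documents do not say which, nor whether it would differ between arms.

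**The case against.** The strongest reply is that the plan already captures early fistulas. Interim findings are recorded, the form has a field for them, and a repeated problem is entered once per subject. The three-month visit is mandatory for everyone, with a reminder, and nothing excuses a woman with a fistula. All of this stands, and it makes loss less likely. It does not say what happens to a recorded fistula when the mandatory entry is nevertheless missing. The plan allows 10% for dropout and, under Problems Anticipated, foresees difficulty with attendance by poor or distant women.

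A second reply is that a fistula would also appear in the adverse-event register. It probably would, but nothing links that register to the secondary-outcome analysis.

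A third is that little inference is at stake. Even fully counted, 2/107 against 0/107 gives a two-sided Fisher p of 2 × (107 × 106)/(214 × 213) = 0.50. That is right about significance testing. The point concerns correct counting of a stated outcome.

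A reader might also infer more than the documents support:
- *That fistula is not analysed at all.* The subject of the sentence in item IV is the follow-up of fistula cases, which fits the referral to the urologist. The broader reading conflicts with the outcome list, the work-up and the form.
- *That having a fistula triggers the exclusion.* The trigger is a missing last entry, and it applies to every woman.
- *That referral takes women out of trial follow-up.* The referral sentence follows directly on the three-month cystography. An early referral that replaces the visit is conjecture.

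**Conclusion.** The concern holds in a limited form. As written, the last-entry rule discards a fistula confirmed after discharge but before three months when the woman has no three-month entry, and nothing else in the plan restores it to the analysis. A fistula found in hospital falls outside that rule and is exposed only through the wider wording in Statistical analysis.

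A claim that the fistula rate is biased downward, or more so in one arm, would go too far: it needs attendance figures that the documents do not give. The percentages under the check rest on assumed values of k and q and on independence between women.

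This is a defect in the rules for one secondary outcome. It is worth correcting because it can lose observed events and the correction is nearly free.

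**What to change.** Replace the closing sentence of item IV with wording such as:

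> Every fistula confirmed from surgery to three months is counted once, in the assigned arm, whether or not a three-month entry exists. Only treatment and results after referral are outside the scope of the study.

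Then make three further changes:

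1. **Denominator.** Report the main rate over all randomised women in each arm. Give the number per arm without a three-month assessment, and show the rate among women assessed at three months as a sensitivity analysis.
2. **Symptom scores.** Do not exempt fistula cases alone from the last-entry rule, because inclusion would then depend on the outcome. To see the effect on a rate, suppose 11 of 107 women miss the visit and 2 of them had a confirmed fistula. Adding only those two to the 96 completers gives 2/98 = 2.0%, against 2/107 = 1.9%. Keep recorded interim post-discharge data for all women under one rule.
3. **Consistency.** Bring the last-entry rule and the non-attender rule in Statistical analysis into line, so that one rule governs post-discharge outcomes.

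The cost is a few sentences of protocol text and one extra table row or analysis. The form already has the field, and no visit, test or treatment changes. The downside is that women never assessed at three months count in the main rate as having no known fistula. The sensitivity analysis and the stated numbers not assessed make that visible.
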